All collected specimens will be sent directly to the research laboratory for processing, analyses and storage. Patients who develop clinical symptoms for SARS-CoV-2 will have both clinical referral for testing and study blood collected. Additional testing for serology, immunology and other markers will be done later in the study. Samples will be stored in appropriately monitored – 80°C freezers or liquid nitrogen containers in the Division of Infectious Diseases and/or Translational and Clinical Research Center laboratories for testing.

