1.2 Primary and Secondary Aims

Primary Aim

1. To determine if the use of hydroxychloroquine as preventive therapy decreases the rate of acquisition of SARS-CoV 2 infections with clinical COVID-19 disease in Study Participants for each randomized treatment arm as compared to placebo.

Secondary Aims

1. Compare the rates of SARS-CoV 2 infections between the randomized treatment arms and the control arms to determine the effect of HCQ dose in the prevention of COVID-19 viremia and disease.
2. Compare the rates of SARS-CoV 2 infections in the non-randomized comparator arm to the randomized groups to assess the impact of chronic weight-based dosing of HCQ for COVID-19 prevention.
3. To compare the rate of SARS-CoV 2 infections as measured by SARS-CoV 2 serum

IgM/IgG in study participants receiving HCQ versus placebo.

4. To compare the seroprevalence of SARS-CoV 2 IgM/IgG positive samples at study entry and study conclusion in all participants receiving HCQ compared to those receiving placebo.
5. To compare the development of clinical symptoms or COVID-19 diagnosis in participants presenting asymptotically at study entry but identified as seropositive by serology at entry between the randomized treatment arms and comparator arm.
6. To compare the clinical COVID-19 disease need for participants in each treatment arm to require emergency room visit, hospitalization, or ability to stay home without hospitalization.
7. To determine the safety and tolerability of HCQ dosing for preventive strategy against COVID-19.
8. To examine other clinical determinants contributing to the risk of SARS-CoV 2 infection including demographics, work type and location, positive COVID-19 partners, possible exposures and clinical symptoms.
9. Examine the association between HCQ drug levels and development of COVID-19 symptoms or positive test results.
10. To identify immunologic, serological and inflammatory markers associated with acquisition and response to COVID-19 in both HCQ and placebo Participants developing laboratory or clinical confirmed disease.

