6.3 Study Aims, Hypothesis and Proposed Analysis

6.3.1 Primary Aim and Hypothesis

As noted below, the primary aim has been changed to: (based on Study Protocol dated 05/26/2020)

To determine if the use of hydroxychloroquine as preventive therapy decreases the rate of acquisition of SARS-CoV 2 infections [with clinical COVID-19 disease](#) in Study Participants [for each randomized treatment arm](#) as compared to placebo.

From: (based on original Study Protocol, dated at and after 04/06/2020)

To determine if the use of hydroxychloroquine as preventive therapy decreases the rate of acquisition of SARS-CoV 2 infections in Study Participants as compared to placebo.

Primary Hypothesis (P1): Hydroxychloroquine administered daily decreases the rate of acquisition of SARS-CoV 2 infections with clinical COVID-19 disease, compared to placebo; and hydroxychloroquine administered weekly decreases the rate of acquisition of SARS-CoV 2 infections with clinical COVID-19 disease, compared to placebo.

The **primary outcome** will be defined as clinical COVID-19 disease with laboratory confirmation of infection.

Presentation with COVID-19 symptoms during study follow-up (defined as fever $\geq 38^{\circ}$ C, or two or more non-fever symptoms that are new since the baseline) will refer participants to obtain SARS-CoV 2 testing through employee health or participants' primary care physician, with test results documented in their medical record.

Laboratory confirmation of SARS-CoV 2 infection (SARS-CoV 2 test positive) will be defined as at least one positive RT PCR, or both IgM and IgG positive serology. The lab test results can be obtained from (a) study blood samples (IgM and IgG serology), and (b) RT PCR test results ordered by a participant's primary care physician or through employee health.

All participants who test SARS-CoV 2 positive will be followed for at least 30 days after the first positive test for presentation of symptoms.

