6.3.2 Full Analysis Set (FAS)

All randomized subjects who do not have a SARS-CoV 2 positive test at the baseline, have taken at least one dose of study medication and provide at least one post-baseline follow-up during the 8-week treatment period. Participants will be analyzed according to the treatment group to which they were assigned according to Intention to treat (ITT).

6.3.3 Safety Analysis Set:

The safety analysis set will consist of all subjects randomized who receive at least one dose of study medication.

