6.3.4.4 Secondary Aims, Hypotheses and Analyses

S1: To compare the rates of SARS-CoV 2 infection status between the randomized treatment arms and the control arms to determine the effect of HCQ dose in the prevention of COVID-19 viremia and disease.

Secondary Hypothesis (S1): There is a hydroxychloroquine dose effect on acquisition of SARS-CoV 2 infection status, compared to placebo.

The endpoint will be SARS-CoV 2 infection status, defined as 1) no SARS-CoV 2 test positive during study follow up; 2) SARS-CoV 2 test positive (i.e., at least one positive RT PCR, or both IgM and IgG positive serology) without clinical symptoms (“asymptomatic SARS-CoV 2 test positive”) 3) SARS-CoV 2 test positive with clinical symptoms (“symptomatic SARS-CoV 2 test positive”).

The analysis will be conducted using FAS. Ordinal logistic regression will be used and analysis will start testing the overall daily and weekly dose effect, followed by pairwise/subgroup comparisons if an overall dose effect is detected at 0.05 level.

S2: To compare the rates of SARS-CoV 2 infection status in the non-randomized comparator arm to the randomized groups to assess the impact of chronic weight-based dosing of HCQ for COVID-19 prevention.

Secondary Hypothesis (S2): There is weekly /daily HCQ dose effect on acquisition of SARS-CoV 2 infection, compared to patients who were already on HCQ.

The endpoint will be the same as described for S1. The analysis will include all randomized *in FAS and non-randomized study participants with at least one post-baseline follow-up.*

We will first test for treatment selection bias using the data collected at the baseline. Inverse probability treatment weighting (IPTW)/propensity score, or matched sub-cohort will be considered to adjust for imbalanced participant characteristics. A similar analysis to that of S1 will be used for testing hypothesis S2.

S3: To compare the rate of SARS-CoV 2 infections as measured by serum IgM/IgG in participants receiving HCQ versus placebo.

Secondary Hypothesis (S3): There is weekly /daily dose effect on status of SARS-CoV 2 infection as measured by serum IgM/IgG, compared to placebo.

The endpoint will be serum IgG/IgM status at each participant’s study conclusion, classified as:

1. Negative (consistently negative for both serologies)
2. Indeterminate (IgM positive, with IgG consistently negative)
3. Positive (IgM and IgG positive, or IgG positive)

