The analysis will be conducted *using FAS*. Ordinal logistic regression will be used to study the status distribution differences among three Arms. Similar to the analysis for S1, the analysis will start testing the overall dose effect, followed by the pairwise comparison between each treated arm and placebo.

S4: To compare the seroprevalence of SARS-CoV 2 IgM/IgG positive samples at study entry and study conclusion in all participants receiving HCQ compared to those receiving placebo.

Secondary Hypothesis (S4): There is weekly /daily dose effect on change in SARS-CoV 2 seroprevalence at study conclusion from the baseline, compared to placebo.

Serum IgM/IgG status at baseline and at study conclusion will be classified into the three categories described for S3. **The endpoint** will be a change in serum IgM/IgG status (from negative at baseline to indeterminate or positive at study conclusion, or indeterminate at baseline to positive at study conclusion).

The analysis approach described for S1 will be used to study the dose effect on change in serum IgM/IgG status *based on all randomized subjects*.

S5: To compare the development of clinical symptoms or COVID-19 diagnosis in participants presenting asymptotically at study entry but identified as seropositive by serology at entry between the randomized treatment arms and comparator arm.

Secondary Hypothesis (S5): There is dose effect on development of clinical symptoms or COVID-19 diagnosis.

The endpoint will be the same as that defined for P1. This analysis will include all randomized study participants who, at baseline, have positive serology (IgM or IgG) but are clinically asymptomatic. The analysis approach described for S1 will be used for this analysis.

S6: To compare the clinical COVID-19 disease need for participants in each treatment arm to require emergency room visit, hospitalization, or ability to stay home without hospitalization.

Hypothesis (S6): There is dose effect on incidence of ED visit/hospitalization, compared to placebo.

The endpoint will be rate of COVID-related ED visits or hospitalizations (by end of the planned 8-week follow-up period, or within 30 days after SARS-CoV 2 test positive if the positive test occurs <30 days before the end of the planned 8-week follow-up period).

FAS will be considered. The analysis approach described for S1 will be used for this analysis.

S7: To determine the safety and tolerability of HCQ dosing for preventive strategy against COVID-19.

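### S2 drops baseline test-positives from the randomised arms but not from the chronic-HCQ comparator, so a pre-existing infection there can count as an acquired one

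*SAP*

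**What the plan says.** S2 compares infection status between the randomised arms and a non-randomised group already taking chronic HCQ; its hypothesis concerns acquisition of infection. The two sides enter by different rules.

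- **Randomised arms:** through the FAS (SAP 6.3.2), which begins "All randomized subjects who do not have a SARS-CoV 2 positive test at the baseline" and adds at least one dose and at least one post-baseline follow-up.
- **Comparator (SAP 6.3.4.4, S2):** "non-randomized study participants with at least one post-baseline follow-up", and nothing more.

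The endpoint is the three-level S1 status. Its lowest level is "no SARS-CoV 2 test positive during study follow up"; the other two are test positive without and with symptoms. Test positive means "at least one positive RT PCR, or both IgM and IgG positive serology" (SAP 6.3.1, repeated under S1). No conversion from negative is required.

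On adjustment, S2 first tests for selection bias on baseline data, then says that IPTW, a propensity score or a "matched sub-cohort will be considered to adjust for imbalanced participant characteristics". Baseline infection status is not named.

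**The concern.** The FAS is defined only for randomised subjects, so its baseline-negative condition does not carry over to the comparators. S2 repeats one FAS condition for them (a follow-up contact) and omits the one that makes the endpoint a measure of new infection. The randomised arms then contribute new infections only, while the comparator contributes new infections plus any pre-existing ones detected again. With no true difference, chronic HCQ could look worse than the study doses. It could look slightly better if baseline positives are seldom detected again, because they then add to the denominator without adding events.

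S2 is the plan's stated analysis of chronic weight-based dosing, and this distortion comes from the inclusion rule itself, separately from ordinary confounding.

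**Working it through.** **1. Can the miscount occur under the plan as written?**

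- Baseline positives in the comparator are foreseen: Aim 5 (SAP 1.2) speaks of participants "identified as seropositive by serology at entry between the randomized treatment arms and comparator arm". S5 counts those who "have positive serology (IgM or IgG) but are clinically asymptomatic", which is wider than the S2 rule; of those positive on serology, only those with both antibodies meet the S2 definition.
- Results can arrive after enrolment. SAP 6.1 acknowledges a lag in initial results, in a sentence about randomised patients. Protocol section 4 adds: "Additional testing for serology, immunology and other markers will be done later in the study".
- A repeat positive is possible, because blood is taken at baseline, week 4 and week 8 (Protocol 7.3).
- Exclusion criterion 2 (SAP 1.3) bars people who have currently tested positive, so it cannot act on a result not yet returned.
- Participants found positive complete the study at that point, and later blood is voluntary (Protocol section 4). A result returned before the first follow-up therefore removes a comparator from S2; a later result does not.

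The number is reduced but not brought to zero. A positive at baseline alone need not count, since the endpoint refers to follow-up; the miscount needs a second positive.

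**2. The plan's own figures.** SAP 6.4 (original aim) allows for 5-10% baseline positives among the randomised: 900/(1 - 0.10) = 1000 per group, as stated (948 at 5%). Power for 1800 against 900 at 6.8% against 10%, two-sided alpha 0.0497, recomputes to 0.815 against the stated 82%. Neither figure is in dispute.

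**3. Size of the distortion.** Let b be the share of comparators positive at baseline, q the share of these who test positive again in follow-up, and r the true new-infection rate in everyone else. Baseline positives who do not test positive again are taken to have no new infection.

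Apparent comparator rate = b·q + (1 - b)·r

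Spurious risk ratio = that rate / r = 1 + b·(q/r - 1), which exceeds 1 when q > r.

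The documents give neither b for the comparators nor q, so both are assumed. With r = 6.8% (the planned HCQ-arm rate), apparent rate and risk ratio:

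| b | q = 0 | q = 0.25 | q = 0.5 | q = 1 |
|---|---|---|---|---|
| 1% | 6.73% (0.99) | 6.98% (1.03) | 7.23% (1.06) | 7.73% (1.14) |
| 2% | 6.66% (0.98) | 7.16% (1.05) | 7.66% (1.13) | 8.66% (1.27) |
| 5% | 6.46% (0.95) | 7.71% (1.13) | 8.96% (1.32) | 11.46% (1.69) |
| 10% | 6.12% (0.90) | 8.62% (1.27) | 11.12% (1.64) | 16.12% (2.37) |

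Worked cell: b = 10%, q = 0.5 gives 0.10 × 0.5 + 0.90 × 0.068 = 0.1112, and 0.1112/0.068 = 1.64.

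**4. Sensitivity to r.** S2 also counts asymptomatic infection, so r may be higher. At an assumed r = 20% with q = 0.5, the ratio is 1 + 1.5b: 1.015, 1.03, 1.075 and 1.15 for b = 1, 2, 5 and 10%.

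**5. False significance (illustration only).** A two-sided pooled z-test at 0.05, one FAS arm of 900 against an assumed 100 to 300 comparators, equal true rates of 6.8%, and a binary simplification of the planned ordinal model. The rejection probability is 7-9% (b = 5%, q = 0.25), 15-25% (b = 5%, q = 0.5) and 36-66% (b = 10%, q = 0.5). With baseline positives excluded it is 4.7-5.0%.

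**The case against.** The case against accepts the asymmetry and the arithmetic, and disputes evidence, size and weight.

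- **Evidence.** The S5 analysis set names only randomised participants, although Aim 5 mentions the comparator arm. The Protocol sentence on later serology concerns additional testing, and Protocol 7.3 separately says entry samples will be tested. Both points stand and weaken the support for late results, but SAP 6.1 acknowledges the lag and nothing requires a comparator's baseline result before follow-up starts.
- **The baseline check.** S2 first tests for selection bias, so baseline positives might show up as an imbalance. They might, if that variable is examined. Weighting or matching on it could not balance it, however, because the FAS contains no baseline positives by construction. Exclusion is needed.
- **Size.** The 5-10% is a planning figure for the randomised arms: the Protocol describes it as viremia, and SAP 6.4 later reuses it for all FAS exclusions. It is not an estimate for comparators. PCR results come only from clinically ordered tests, so a repeat positive on study blood needs both antibodies again, and q is unknown. If the Protocol's figure of up to 85% asymptomatic or minimally symptomatic infection is applied to 6.8%, r could reach 0.068/0.15 = 45%; with q = 0.5 the ratio is then only 1.001 to 1.010 over b = 1-10%, and with q = 0.25 it is below 1. All of this stands: neither size nor direction is established.
- **Weight.** S2 is secondary and non-randomised, and its hypothesis and endpoint are worded towards new infection. That intention is the reason to align the inclusion rule with it.

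**Conclusion.** The concern holds. As written, S2 excludes baseline positives on one side only, and its endpoint does not require conversion, so a pre-existing comparator infection can be counted as acquired. Confidence is high on the asymmetry and low on its size.

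Under the assumptions shown, the spurious risk ratio is about 1.03 to 1.13 if 1-2% of comparators are positive at entry and a quarter to a half test positive again. It is larger if the randomised-arm planning figure of 5-10% applies, close to 1 if the true infection rate is high, and below 1 if few test positive again. The primary analysis and the 935 per arm are unaffected. The weight is minor to moderate, and the plan should be changed.

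**What to change.** In SAP 6.3.4.4, S2, restrict the non-randomised participants to those with no SARS-CoV-2 positive test at baseline, by the same definition as for the FAS (at least one positive RT-PCR, or IgM and IgG both positive), and at least one post-baseline follow-up. Leave the FAS definition (6.3.2) and S3 as they are. Make the change before database lock, because SAP 6.3.4.1 treats analyses not described by then as post hoc and exploratory.

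The cost is one sentence. Protocol 7.3 already provides for testing the entry samples, so no new procedure is needed. The downside is the loss of a few comparators from a group that SAP 1.4 already expects to be smaller than the randomised arms.

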### **2.4 Secondary Endpoints**

1. The difference of SARS-CoV 2 infections between the randomized treatment arms and the control arms.

2. The difference of SARS-CoV 2 infections in the non-randomized comparator arm to the randomized groups.
3. The rate of SARS-CoV 2 infections as measured by IgM/IgG seroconversion in study participants receiving randomized HCQ versus placebo.
4. The seroprevalence of SARS-CoV 2 IgM/IgG positive samples at study entry and study conclusion in all participants receiving HCQ compared to those receiving placebo.
5. Emergence of clinical symptoms or COVID-19 diagnosis in participants presenting asymptotically at study entry but identified as seropositive by serology at entry between the randomized treatment arms and comparator arm.
6. To examine the level of care needed by participants in each arm developing COVID-19 as measured as requiring emergency room visit, hospitalization or able to stay home without hospital care.
7. The safety and tolerability of HCQ dosing for preventive strategy against COVID-19 as measured by adverse events and serious adverse events.

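### S3 counts IgG alone at study end as infection but keeps baseline IgG-only participants, so it does not measure the protocol's seroconversion endpoint (minor, one secondary endpoint)

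*SAP*

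**What the plan says.** **The S3 endpoint.** Protocol 2.4, secondary endpoint 3, is the infection rate "as measured by IgM/IgG seroconversion in study participants receiving randomized HCQ versus placebo". In SAP 6.3.4.4 the S3 endpoint becomes a status: "The endpoint will be serum IgG/IgM status at each" participant's study conclusion, in three ordered categories. The highest is "Positive (IgM and IgG positive, or IgG positive". The analysis set is the FAS and the method is ordinal logistic regression, with an overall dose test first. S3 has no baseline-negative condition and no baseline serology covariate.

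**The analysis set.** SAP 6.3.2 defines the FAS as "All randomized subjects who do not have a SARS-CoV 2 positive test at the baseline", plus at least one dose and one follow-up.

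**What counts as positive.** SAP 6.3.1 says laboratory confirmation "will be defined as at least one positive RT PCR, or both IgM and IgG positive serology", and S1 repeats this. No other definition of a positive test is given.

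**Single-antibody positives at entry are expected.** S5 is built on randomized participants who, at baseline, "have positive serology (IgM or IgG) but are clinically asymptomatic".

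**The concern.** S3 uses two different thresholds. At baseline, IgG alone is not enough to remove a participant from the FAS. At study end, IgG alone is enough to make that participant Positive. Someone infected before enrolment, with IgG but no IgM at entry, is therefore scored as an S3 infection if the antibody persists.

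The S3 rate is then a mixture of old and new infection. Study drug cannot have prevented the old ones, and randomization spreads them evenly across arms. They add the same amount to each arm's rate, pull the risk ratio towards 1 and add noise. A real effect on new infection would be understated and could be missed, and the reported result would not be the seroconversion comparison named in the protocol. Baseline IgM-only participants raise a parallel problem: they also stay in the FAS and can finish as Indeterminate or Positive.

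**Working it through.** **Inputs from the SAP (6.4).** Rates of 10% on placebo and 6.8% on HCQ; 935 per arm; two-sided 0.05 at the final look. For S1 to S4 taken as binary, the SAP points to Method #3: both HCQ arms combined (1,870) against placebo (935) in a single test.

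**Assumptions.**
- The IgG-only share at baseline, *q*, is not given in either document. I use 1% to 10%.
- IgG present at entry persists to study end.
- The SAP's clinical-disease rates stand in for new seropositivity.
- The ordinal endpoint is collapsed to binary.

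**Step 1: reproduce the SAP's power.** With a pooled null variance, power = Φ[(p0 − p1 − 1.96·SE0)/SE1].
- Pooled rate = (935 × 0.10 + 1870 × 0.068)/2805 = 0.0787
- SE0 = √[0.0787 × 0.9213 × (1/935 + 1/1870)] = 0.01078
- SE1 = √[0.10 × 0.90/935 + 0.068 × 0.932/1870] = 0.01141
- Power = Φ[(0.032 − 1.96 × 0.01078)/0.01141] = Φ(0.95) = 0.830, against 0.835 in the SAP's Table 1. At 900 per arm the result is 0.816, against 0.819. Both reproduce.

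**Step 2: dilution under S3 as written.** If a share *q* of each arm is already IgG positive and stays so, the observed rate is q + (1 − q)p. At q = 5%:
- Placebo: 0.05 + 0.95 × 0.10 = 0.145
- HCQ: 0.05 + 0.95 × 0.068 = 0.1146
- Risk ratio = 0.1146/0.145 = 0.79
- Power = Φ[(0.0304 − 1.96 × 0.01323)/0.01367] = Φ(0.33) = 0.628
- Share of placebo positives that are old infections = 0.05/0.145 = 34%

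**Step 3: restrict to baseline-negative participants.** The share *q* leaves, so n becomes 935(1 − q) per arm and the rates return to 10% and 6.8%.

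| q (assumed) | Placebo vs HCQ, S3 as written | Risk ratio | Power as written | Power if restricted |
|---|---|---|---|---|
| 0 | 10.0% vs 6.8% | 0.68 | 83% | 83% |
| 1% | 10.9% vs 7.7% | 0.71 | 79% | 83% |
| 2% | 11.8% vs 8.7% | 0.73 | 74% | 82% |
| 5% | 14.5% vs 11.5% | 0.79 | 63% | 81% |
| 10% | 19.0% vs 16.1% | 0.85 | 48% | 79% |

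**Step 4: a higher infection rate.** Serology also picks up asymptomatic infection, so new seropositivity could exceed the clinical-disease rate. With assumed rates of 20% versus 13.6% (again a ratio of 0.68), power falls from 99% to 98/96/91% at q = 2/5/10%. The estimate is still attenuated: 15.3/21.6 = 0.71, 17.9/24.0 = 0.75 and 22.2/28.0 = 0.79.

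**Step 5: type I error.** With equal true rates of 10% in all arms, simulated rejection by Method #3 is 0.050 at q = 0, 5% and 10%.

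**Step 6: does S4 share the problem?** S4 counts only moves up from negative or indeterminate at baseline. A baseline IgG-only participant is already Positive and cannot be an event, so the rates are (1 − q) × 10% and (1 − q) × 6.8%, and the ratio stays 0.68. At 1,000 randomized per arm, power is 84.5/83.4/81.2% at q = 2/5/10%.

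**The case against.** **S4 already does this.** It classifies serology at baseline and at study end with the same three categories and counts transitions, in all randomized subjects. A reader might infer that the trial has no clean serological comparison. The documents do not support that: S4 is prespecified and undiluted (step 6). This objection stands and confines the harm to S3. It does not remove the point, because S3 would still be reported as the serological infection rate and is the aim that matches the protocol's seroconversion endpoint.

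**The loss could be quoted as larger.** A pairwise test at 900 per arm starts at 69% power and falls to 59/48/36% at shares of 2/5/10%. S3 starts with an overall test, and the SAP's power text links S1 to S4 to Method #3 with 935 per arm, so the figures in the working are the relevant ones.

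**The inputs are soft.** This stands. The 5–10% in SAP 6.4 refers to people positive at baseline or otherwise excluded from the FAS, not to IgG-only participants who remain. Depending on the infection rate, the power loss runs from trivial to material.

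**Entry criteria may screen these people out.** SAP exclusion 2 bars a current positive serology test. It can act only on results known at entry. Protocol section 4 places study serology later, and SAP 6.1 expects some randomized participants to be found positive at baseline afterwards.

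**The FAS wording may mean any positive antibody.** SAP 6.3.2 does not cross-refer to 6.3.1. If any positive antibody were meant, the IgG-only dilution would vanish. The SAP does not say so, and 6.3.1 supplies the only definition.

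**Conclusion.** The point holds as a minor one, on a single secondary endpoint. Read with the only definition of test positive in the SAP, S3 counts baseline IgG-only participants as infections and does not measure the seroconversion endpoint in Protocol 2.4.

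The consequence is attenuation and lost power. At 10% versus 6.8% and an assumed IgG-only share of 1% to 10%, the risk ratio drifts from 0.68 to between 0.71 and 0.85, and power drops from 83% to between 79% and 48%. At 20% versus 13.6% the power loss is small. These sizes depend on the assumed share, on IgG persisting, on the stand-in event rates and on a binary endpoint.

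Two stronger inferences are not supported. S3 is not at risk of a false-positive finding from this cause, because old infections are balanced by randomization. Nor does the mismatch extend to the primary outcome: that outcome applies the 6.3.1 definition during follow-up, the same threshold that the FAS applies at baseline.

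**What to change.** In SAP 6.3.4.4, add one sentence before database lock: S3 is analysed in FAS participants who are negative for both IgM and IgG at baseline, so that the endpoint is seroconversion as in Protocol 2.4. The restriction uses a pre-treatment measurement, so the randomized comparison is preserved. S4 already needs baseline serology, so no new data are required. A short cross-reference in 6.3.2 to the definition in 6.3.1 would also settle how the FAS rule is to be read.

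The cost is a slightly smaller S3 set, for example 935 × 0.95 = 888 per arm at a 5% IgG-only share, and somewhat fewer once baseline IgM-only participants also leave. Some of the IgM-only group may be early infections. Their move to IgG positive is lost from S3 but is still counted in S4.

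### The endpoint and analysis set for secondary aim S5 do not match the aim: symptoms-or-diagnosis becomes symptoms-and-confirmation, and the comparator arm is left out

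*SAP*

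**What the plan says.** SAP 6.3.4.4 gives the S5 aim as "To compare the development of clinical symptoms or COVID-19 diagnosis in participants presenting asymptotically at study entry", restricted to those "identified as seropositive by serology at entry between the randomized treatment arms and comparator arm". The hypothesis keeps the either/or outcome but names no comparator arm: "There is dose effect on development of clinical symptoms or COVID-19 diagnosis". The same aim is in SAP 1.2 and Protocol 2.2 (item 5), and Protocol 2.4 lists it as secondary endpoint 5.

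The analysis is then fixed in two sentences. On the outcome: "The endpoint will be the same as that defined for P1". On the population: "This analysis will include all randomized study participants who, at baseline, have positive serology (IgM or IgG) but are clinically asymptomatic". The method is borrowed from S1: ordinal logistic regression, with an overall dose test at 0.05 followed by pairwise comparisons.

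SAP 6.3.1 defines the P1 outcome as "clinical COVID-19 disease with laboratory confirmation of infection". Confirmation means "at least one positive RT PCR, or both IgM and IgG positive serology", where serology comes from study blood samples and PCR results come from the participant's own care. The symptom rule, written as the trigger for referral to testing, is fever of at least 38°C or "two or more non-fever symptoms that are new since the baseline".

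**The concern.** Three things do not line up.

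- **Outcome.** The aim joins symptoms and diagnosis with *or*. P1 joins them with *and*.
- **Comparison.** The aim names the comparator arm. The analysis set excludes it.
- **Timing.** P1 was written for people who start without a positive test. S5 applies it to people chosen because they start with one, and nothing says that the confirming result must be new.

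At stake is one protocol-listed secondary endpoint. Followed as written, the SAP yields no comparator-arm estimate for it. It also yields an event rate in the randomised arms that blends symptom incidence with newly confirmed infection, in proportions set by the antibody pattern at entry.

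**Working it through.** The documents give no sample size, event rate or power for S5, so there is no stated figure to reproduce. The check is a comparison of texts, followed by a rough look at precision.

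**1. Which arm is the comparator?** Protocol 4 and 6.1 and SAP 1.1, 1.4 and 6.1 all use the word for the fourth, non-randomised group on chronic HCQ. S1 refers to control arms instead. S2 expressly adds the non-randomised participants and plans inverse probability weighting, propensity scores or matching for them. S5 does neither.

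**2. What does P1 require in each S5 stratum?** Everyone in S5 is asymptomatic at entry. I take the SAP 6.3.1 symptom rule as the clinical part of P1, because no other definition is given.

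| Serology at entry | Laboratory part at entry | What makes a P1 event |
|---|---|---|
| IgM and IgG both positive | Can already be met | New fever, or at least two new non-fever symptoms |
| Only one positive | Not met | The same symptoms plus a positive PCR or the second antibody |

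Under the aim, new symptoms alone would count in both rows. Under P1 they do not count in the second row without a confirming test.

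**3. Why does P1 itself escape this?** The full analysis set (SAP 6.3.2) removes anyone with a positive test at baseline. S5 does not use that set.

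**4. How large is the subgroup?** Unknown. The nearest figure is 5-10%, and it stands for three different things: viremia at baseline (Protocol 8.3), SARS-CoV-2 positivity at baseline (SAP 6.4, original aim) and exclusion from the full analysis set (SAP 6.4, revised aim). None is the share with IgM or IgG positive. Purely as an assumption, 0.05 × 1000 = 50 and 0.10 × 1000 = 100 per arm.

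**5. Precision under that assumption.** Borrow the SAP's rates p0 = 0.10 and p1 = 0.068, with two-sided 0.05 and mean rate p̄ = 0.084:

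power = Φ{[(p0 − p1)√n − 1.96√(2p̄(1 − p̄))] / √(p0(1 − p0) + p1(1 − p1))}

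- n = 50: (0.2263 − 0.7689) / 0.3916 = −1.386, so power is about 8%.
- n = 100: (0.3200 − 0.7689) / 0.3916 = −1.146, so power is about 13%.
- Both doses pooled against placebo: about 11% and 17%.
- Placebo rates of 20% to 50% with the same 32% relative reduction, one dose against placebo: about 13% to 37% at 50 per arm, and 23% to 63% at 100 per arm.

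These figures are not the defect. They show how much any version of S5 could deliver.

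**The case against.** The best defence is that the S5 hypothesis claims only a dose effect, which the three randomised arms can test. Nobody meets the whole P1 endpoint at entry, because all are asymptomatic. Serology at entry precedes treatment, so the antibody mix is balanced across arms in expectation. For double-positives the endpoint falls back to new symptoms, which is one half of the aim. All of this stands. A reader might infer that S5 cannot answer its question at all, or that its randomised comparison is biased. The documents support neither reading.

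A second defence is that the SAP never says a baseline result counts as confirmation. P1 speaks of acquiring infection, and S1's endpoint is framed around positives during follow-up. That is fair: the timing is unspecified, and counting the entry sample is one reading. But S5 takes its endpoint from P1 and only its method from S1. A follow-up rule alone would not settle it either, since a double-positive whose antibodies were both still detectable in the week 4 sample would have a positive result during follow-up without any new infection.

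Third, the matter is small: S5 is one of ten secondary aims, no power claim rests on it, and S2 already analyses the comparator arm. This limits the importance. S2, however, is not an analysis of people seropositive at entry, so it does not supply the missing comparison.

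**Conclusion.** The mismatch is real and can be read directly from the text. As written, S5 gives no comparator-arm estimate. It does not count single-antibody participants who develop symptoms without a confirming test. Its one endpoint can mean new symptoms in double-positives and symptoms plus a new positive result in single-positives. The last point rests on the absence of any rule in SAP 6.3.1 that the confirming test be new since baseline.

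The consequence is limited to the interpretation of one secondary aim. The randomised dose comparison is unbiased, and P1 is protected by the full analysis set. A reader might also take 50 to 100 per arm as the SAP's own estimate for S5. It is not: it borrows a percentage given for other quantities. The exclusion of people already known to be seropositive (SAP 1.3) could lower the number, and counting single-antibody positives could raise it. The double-positive share, which governs how mixed the endpoint is, appears nowhere.

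**What to change.** Give S5 its own endpoint, with two components reported separately:

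- **(a) Symptoms** new since baseline, by the SAP 6.3.1 rule (fever, or at least two new non-fever symptoms).
- **(b) Diagnosis** confirmed by a test dated after baseline: a positive RT PCR, or new conversion to positivity on both antibodies among those not already double-positive at entry. For double-positives only PCR can then confirm.

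For the comparator arm, choose one of two courses. Either add its baseline-seropositive members, with S2's selection adjustment where numbers allow and descriptively otherwise, or delete that arm from the aim in both the SAP and the Protocol.

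The cost is wording only, with no new visits or samples. There are two downsides. Numbers will be small and estimates imprecise. Component (a) can also pick up drug effects: nausea, vomiting and headache are among the side effects in Protocol 10.3 and also among the COVID-19 symptoms in Protocol 6.2.1. That overlap is the reason to keep the two components apart.
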